Abbreviations: CGI-I=Clinical Global Impression–Improvement; LS =least squares; MBA=Motor Behavior Assessment; mITT=modified Intent-to-treat; PR=placebo response; RSBQ=Rett Syndrome Behaviour Questionnaire; RTT-DSC=RTT Domain Specific Visual Analog Scale; TBL=treatment Baseline; UnAdj=unadjusted

^a Prespecified model covariates if $p \leq 0.1$: TBL and/or PR.

[figure not shown]
^b CGI-I has no pretreatment baseline value. The CGI-I values at Day 14 are the ratings of change from Day 0 (the pretreatment Baseline) to Day 14 (end of placebo run-in).

Among the three outcome measures that exhibited improvement compared to placebo for the 200 mg/kg BID group, the median magnitude of effect (change) was 15% for RTT-DSC (vs. 5% for placebo) and the mean magnitude of effect (change) was 16% for RSBQ (vs. 6%

for placebo). For the CGI-I, the mean outcome was 3.0 for the 200 mg/kg BID group and was 3.5 for placebo. For the CGI-I, more than 20% of subjects in the 200 mg/kg BID group were judged by clinicians to be “much improved”, compared with less than 5% of those on placebo.

At the end of the dosing period, data indicate that clinical benefit (change from treatment Baseline) was continuing to accrue and that there was a divergent trend between the placebo and 200 mg/kg BID groups as highlighted below in Figure 1–1 for the RSBQ. Further, there is evidence of a significant diminution of effect following cessation of dosing, suggesting that the separation during the dosing period was due to beneficial treatment effect and not from other differences between the two arms that occurred simply by chance.

Figure 1–1 Comparison of Change from Treatment Baseline on the RSBQ at Follow-Up Assessments Between 200 mg/kg BID and Placebo BID Treatment Groups

Abbreviations: BID=twice daily; LS=least squares; RSBQ=Rett Syndrome Behaviour Questionnaire
Note: End of treatment assessment is at Day 54. Treatment baseline is at Day 14, at the end of the placebo run-in. Day 66 is post-treatment.

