3.1.1 Open-label Treatment Period (40 Weeks)

The Week 12/EOT visit of the antecedent study (ACP-2566-003) generally serves as the Baseline visit (Visit 1) of the present study.

Those subjects for whom it is not possible to use the Week 12/EOT visit of the antecedent study (ACP-2566-003) as the Baseline visit (Visit 1) may be re-evaluated for study eligibility at the Baseline visit of the present study, with approval by the Sponsor or Medical Monitor. Those subjects will have blood drawn for Baseline values 3 to 14 days before the Baseline visit. These subjects include: 1) those who were discontinued from Study ACP-2566-003 before completion because of the COVID-19 public health emergency; and 2) those who completed Study ACP-2566-003, but were prevented from entering this study because of the COVID-19 public health emergency.

All efficacy assessments (except the CGI-I) will be completed at the Baseline visit prior to administration of the first dose of study drug in the present study ([Table S-2](#)).

The first dose of study drug for the present study is intended to be administered after all Baseline assessments are completed. Since in most cases, the subject will have taken the last dose of study drug from the antecedent study on the morning of the Baseline visit for this study, the first dose of study drug for this study will then be administered either as an evening dose after the Baseline visit has been completed or on the following day. A triplicate electrocardiogram (ECG) must be performed 2-3 hours after the first dose and a PK sample will be taken upon completion of the ECG.

Study drug must be discontinued at any time in the study in the event that a post-enrollment QTcF duration of ≥ 500 ms or an increase of ≥ 60 ms compared to the average QTcF interval at Baseline of the present study (before dosing) is observed. For visits at which more than one ECG is completed, the average QTcF interval of all legible ECGs will be used to determine the QTcF interval for that visit.

The dose will be administered according to [Section 5.1.3](#). Dosing is twice a day, once in the morning and once in the evening.

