4.1 Inclusion Criteria

A subject must meet all of the following inclusion criteria to be eligible for participation in the study:

1. Informed consent prior to the conduct of any study procedures is required as follows:
 - a. For subjects who are minors: written informed consent will be obtained from the legally acceptable representative (LAR). The subject should provide written or oral assent if deemed able by the Investigator. The process of obtaining informed consent will be conducted in accordance with institutional review board (IRB) or ethics committee (EC) policy and applicable local law.

- b. For subjects who are not minors: written informed consent will be obtained from the LAR or the subject if deemed able by the Investigator. If the subject is deemed not able to provide consent, the subject should provide written or oral assent if deemed able by the Investigator. The process of obtaining informed consent will be conducted in accordance with IRB or EC policy and applicable local law.
 - c. The subject's caregiver must also provide written informed consent regarding their participation in the study prior to participating in any study procedures.
2. Has completed the Week 12/EOT visit of the antecedent study, Study ACP-2566-003
NOTE: An exception is made for subjects who either discontinued from or completed but did not directly rollover from the antecedent study due to the COVID-19 public health emergency. These subjects may enroll in this study within 12 months of their withdrawal/completion from the antecedent study, with approval of the Sponsor or Medical Monitor.
3. Met all entry criteria for the antecedent study
4. May benefit from long-term treatment with open-label trofinetide in the judgment of the Investigator
5. Can still swallow the study medication provided as a liquid solution or can take it by gastrostomy tube
6. The subject's caregiver is English-speaking and has sufficient language skills to complete the caregiver assessments

Childbearing Potential

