3. STUDY DESIGN

3.1 General Study Design

This is a 40-week, multicenter, open-label extension (OLE) study to evaluate long-term safety and tolerability of trofinetide in girls and women with Rett syndrome. Subjects who complete the preceding double-blind study (ACP-2566-003) will be eligible to enroll in the OLE.

The Week 12/EOT visit of the antecedent study will serve as the Baseline visit of the present study. The data gathered at the Week 12/EOT visit of the antecedent study serves as the baseline data of the present study.

Because of the special circumstances surrounding the Coronavirus Disease 2019 (COVID-19) public health emergency in the spring of 2020, subjects who were discontinued from Study ACP-2566-003 before completion because of the COVID-19 public health emergency and subjects who completed Study ACP-2566-003, but were prevented from entering the present study because of the COVID-19 public health emergency, may be re-evaluated for eligibility at the Baseline visit of the present study.

However, subjects who are discontinued from Study ACP-2566-003 for other reasons other than COVID-19 pandemic, or who are not able to rollover to this study at the Week 12/EOT visit of the antecedent study, will not be able to enter the present study.

[figure not shown]
The duration of participation for individual study subjects will be approximately 44 weeks. Approximately 28 sites will participate in this study.

The study will have two periods ([Figure 1](#)):

- Treatment period: 40 weeks
- Safety follow-up period: 30 days

The study design is summarized in Figure 1.

Figure 1 Schematic of Study Design

^a Subjects who roll over into the subsequent open-label study (ACP-2566-005) will not have the safety follow-up telephone call or telemedicine visit.

The schedule of events and assessments is provided in the appendix ([Section 21.1](#)). As shown in the schedule of events, study visits may be done off-site rather than in the clinic with the prior approval of the Sponsor or Medical Monitor.

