5.1 General Data Reporting Conventions

Continuous variables will be summarized using the following descriptive statistics: number of subjects, mean, standard error (SE), standard deviation (SD), median, minimum, and maximum. For descriptive summaries of efficacy, the 95% confidence interval (CI), calculated as $\text{mean} \pm 1.96 * \text{SE}$, will be presented. Unless specified otherwise, means, medians, and CIs will be presented to one more decimal place than the raw data, and the SDs and SEs will be presented to two more decimal places than the raw data. In general, the maximum number of decimal places is 4 and values will be truncated to 4 decimal places in situations where there are more than 4 decimal places. Wherever possible data will be decimal aligned.

Height, weight and BMI will be presented with a maximum of one decimal place.

Categorical variables will be summarized by the number of subjects and the percentage of subjects in each category; the number of subjects and the percentage of subjects with missing data will be summarized for demographic and baseline characteristics (if applicable). Categories with zero counts will not have zero percentages displayed. For demographic summaries, percentages will be calculated by using the total number of subjects in the given treatment group of the antecedent study as the denominator. Percentages will be presented with one decimal place.

Duration in months will be calculated as ([the number of days / 365.25] *12).

Lab values, not including PK concentration data, that are collected with “<” or “>” signs will generally be analyzed as the numerical value without the sign in tables and figures. In listings, these data will be reported as collected with the sign.

For each continuous measure in safety and efficacy analyses, change from baseline results will be presented by treatment group of the antecedent study and overall in two ways:

1. Main analysis: using the baseline of this study, as defined in [Section 5.5](#), to report the changes across the timepoints of this open-label Study ACP-2566-004.
2. Exploratory analysis: using the baseline from the antecedent study, ACP-2566-003, to report the changes across the timepoints of this open-label Study ACP-2566-004.

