5.4 Baseline Definition

Data from the latest predose value of (Study ACP-2566-003 Week 12/EOT visit, unscheduled visit within Week 12 window, visit within 2 weeks of last double-blind dose, or Study ACP-2566-004 Baseline Visit) will be carried over as Baseline information in the present study, as applicable (e.g., not for the CGI-I for which this is not applicable).

Subjects for whom the Baseline visit of this study is not on the same day as the Week 12/EOT visit of the antecedent study (e.g., subjects in the antecedent study who were prevented from entering this study by the COVID-19 public health emergency) will have blood drawn for Baseline values three to fourteen days before the Baseline visit.

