14. SAFETY ANALYSES

All safety analyses will be performed using the Safety Analysis Set. Safety summaries will be summarized using descriptive statistics by treatment group of the antecedent study and overall. For each continuous measure in clinical laboratory variables, vital signs, and electrocardiogram, change from baseline results will be presented in two ways as specified in [Section 5.1](#).

The primary safety endpoints are:

- Treatment-emergent adverse events (TEAEs)
- Serious adverse events (SAEs)
- Withdrawals due to adverse events (AEs)
- Potentially clinically important changes in other safety assessments

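### The former-trofinetide column pools uninterrupted rollovers with any COVID-exception subjects who restart after a gap of up to 12 months, and no planned summary separates them

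*SAP*

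**What the plan says.** **Entry.** For most subjects the Week 12/EOT visit of ACP-2566-003 is also the Baseline visit here. Protocol 3.1.1 expects that "the subject will have taken the last dose of study drug from the antecedent study on the morning of the Baseline visit", with open-label drug starting that evening or the next day. The exception covers subjects who were discontinued from ACP-2566-003 because of COVID-19, or who completed it but could not roll over. They "may be re-evaluated for eligibility at the Baseline visit of the present study" (SAP 3.1), and Protocol 4.1, criterion 2, adds: "These subjects may enroll in this study within 12 months of their withdrawal/completion from the antecedent study". The exception does not depend on prior arm. Protocol 3.1 closes it to later cases.

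**Baseline.** Protocol 9.5.1 does not carry Week 12/EOT data forward for these subjects. SAP 5.4 takes the latest predose value, which for them is the new Baseline visit.

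**Tables.** The Safety Analysis Set is everyone dosed (SAP 4). In SAP 5.1, "change from baseline results will be presented by treatment group of the antecedent study and overall in two ways": from the present Baseline (main) and from the ACP-2566-003 baseline (exploratory). SAP 13.1 tabulates efficacy by ACP-2566-003 arm. SAP 14 states: "Safety summaries will be summarized using descriptive statistics by treatment group of the antecedent study and overall". The only subgroup in SAP 12.5 is *MECP2* mutation grouping. SAP 3.6 relates COVID-19 to early terminations, deviations, medications and adverse events, but not to entry route or time off drug. Exposure in SAP 10.1 counts dosing in this study only.

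**The concern.** Two kinds of subject share the former-trofinetide column. A direct rollover's change from Baseline shows what happens when treatment continues. A re-entrant's change shows what happens when treatment is restarted after a break.

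The Protocol gives its own reason to expect a difference. Of the second Phase 2 study, Protocol 1.3 says "there is evidence of a significant diminution of effect following cessation of dosing". A subject who has lost benefit during a gap can regain it on restarting, and in this column that would read as further improvement on long-term treatment. CGI-I is exposed in the same way, because it is rated against the present Baseline. TEAE incidence, a primary endpoint, would combine events during continued dosing with events after a restart.

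The exploratory analysis has a different problem. Its Week 40 lies at different distances from the ACP-2566-003 baseline for the two kinds of subject, and a re-entrant's interval includes an untreated stretch.

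**Working it through.** The plan states no figure to reproduce: about 180 subjects are expected, and the number is not based on power. The check traces the rules and then illustrates size under stated assumptions.

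**1. Is a re-entrant off drug at Baseline?** No bridging supply is described. Protocol 1.3 gives a half-life of 5.3 to 6.1 h. The fraction remaining is 0.5^(gap / half-life). For a 3-day gap:
- 72 / 6.1 = 11.8 half-lives, 0.028% remaining
- 72 / 5.3 = 13.6 half-lives, 0.008% remaining

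A gap of even a few days therefore gives an off-drug Baseline.

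**2. Does any planned summary separate the two groups?** The analysis set includes both, the columns follow ACP-2566-003 arm, and neither the subgroup nor the COVID-19 breakdowns use entry route. None does.

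**3. Possible shift in mean RSBQ change.** Let f be the share of re-entrants in the column, m the mean change in continuing subjects and r the mean change in restarters. Column mean = (1 − f)m + f·r, so the shift is f(r − m).

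Assumptions: m = 0; r = −4.4, the Phase 2 difference at 200 mg/kg BID (−6.7 − (−2.3), Protocol Table 1–1), or r = −6.7, the whole within-group change. Lower RSBQ is better. The shares f are not in the documents.

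| f | r = −4.4 | r = −6.7 |
|---|---|---|
| 5% | −0.22 | −0.34 |
| 10% | −0.44 | −0.67 |
| 20% | −0.88 | −1.34 |

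If continuing subjects also improve, r − m shrinks and so does the shift.

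**4. Scale.** From Table 1–1, a difference of 4.4 with p = 0.042 and n = 24 and 27 implies t ≈ 2.09 (49 df, ignoring the covariate). SE = 4.4 / 2.09 ≈ 2.11, and SD ≈ 2.11 / √(1/24 + 1/27) ≈ 7.5. With an assumed column of 90 (half of 180; the actual split is not given), SE ≈ 7.5 / √90 ≈ 0.79 and the 95% half-width is 1.96 × 0.79 ≈ 1.55 points. Every shift in the table lies inside that half-width.

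**5. Diarrhea, as an illustration for TEAEs.** Assume restarters have the Phase 2 rate of 56% at 200 mg/kg BID. For continuing subjects assume 4%, 13% or 27%, the other Phase 2 group rates, used only to span a range. Column rate = (1 − f)·continuing + f·56%.

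| f | continuing 4% | 13% | 27% |
|---|---|---|---|
| 5% | 6.6% | 15.2% | 28.5% |
| 10% | 9.2% | 17.3% | 29.9% |
| 20% | 14.4% | 21.6% | 32.8% |

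**6. Exploratory analysis.** Time from the ACP-2566-003 baseline to Week 40 is 12 + 40 = 52 weeks for a direct rollover. For a completer who re-enters at exactly 12 months it is 12 + 52 + 40 = 104 weeks. The second figure is a ceiling.

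**The case against.** The strongest reply is that this may concern very few subjects. The exception is closed to later cases, neither document counts those admitted, and only the former-trofinetide part matters for the main analysis. The 5% to 20% shares are assumptions, and nothing supports the upper end. The RSBQ shifts fall within the sampling uncertainty of the column, the analyses are descriptive, and efficacy is secondary. All of that stands and limits the size. It does not show that the column contains one kind of subject.

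Other objections also stand in part:
- The column is not constant-dose treatment even without re-entrants, because the assigned dose may change with weight at Baseline or rise after an earlier reduction. Restricting to direct rollovers isolates uninterrupted dosing, nothing more.
- All data are listed, so re-entrants could be found from dates. But a listing does not alter a mean or an incidence.
- Table specifications are in a separate document that is not available here. The grouping rule, however, is set in the SAP.

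A reader might infer that this column is the study's only evidence on long-term treatment. It is not: former-placebo subjects also contribute up to 40 weeks. What the former-trofinetide column adds is about 52 weeks of continuous exposure.

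A reader might also infer that restarters will have gastrointestinal events again. The documents contain no re-challenge data. For the first Phase 2 study, at lower doses, Protocol 1.3 reports no time-related or dose-related pattern of adverse events. Recurrence is plausible but unproven, so the diarrhea table is only an illustration.

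**Conclusion.** The point holds as a matter of what the column contains. Former-trofinetide subjects with on-drug and off-drug Baselines are tabulated together, and change from Baseline, CGI-I and TEAE incidence mix continuation with re-initiation to whatever extent re-entrants are present.

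The size cannot be determined and may be small. The RSBQ shift of about 0.2, 0.4 or 0.9 points rests on assumed shares of 5%, 10% and 20%, on restarters regaining the Phase 2 difference of 4.4 points, and on continuing subjects staying level. The stronger reading, that the former-trofinetide results are materially biased, is not supported without a count of re-entrants.

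Nor do the documents support taking these subjects out of the planned tables. Protocol 9.4 applies the Safety Analysis Set to all analyses. A 14-day rule for calling a subject continuing would also be poorly grounded. SAP 5.4 uses "visit within 2 weeks of last double-blind dose" to qualify a baseline assessment, not to define a dosing gap, and the Phase 2 loss of effect rests on Day 66, only 12 days after treatment ended on Day 54.

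**What to change.** Keep every planned Safety Analysis Set table. In SAP 5.1, 13.1 and 14, add:

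1. A flag for entry route (direct rollover or COVID-exception re-entry), with the number of days from last double-blind dose to first open-label dose.
2. The number of re-entrants and their gap length, by ACP-2566-003 arm.
3. Supplementary tables of the main efficacy changes, CGI-I and TEAEs by ACP-2566-003 arm, restricted to direct rollovers. Re-entrants are shown separately, or listed if few.
4. The same direct-rollover-only sensitivity table for the exploratory change from the ACP-2566-003 baseline, covering both arms.

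Protocol 9.5.5 already allows subgroup analyses to be specified in the SAP. The flag uses dose dates that the plan already relies on. The cost is one derived variable and a few extra tables with a slightly smaller n. If there prove to be few re-entrants, the count and a listing will show that the planned column can be read almost as it stands.

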5.2 Derived Efficacy Variables

In general, assessment total scores and subscores will be derived within the analysis datasets. In the event that total scores and/or subscores are also collected on the electronic case report from

(eCRF), the derived values will be used for all analyses. Both the raw and derived scores will be presented in listings.

5.2.1 Rett Syndrome Behaviour Questionnaire (RSBQ)

The RSBQ is a 45-item caregiver-completed rating scale in which the caregiver rates items as “0” (Not True), “1” (somewhat or sometimes true) or “2” (very true). The RSBQ includes 8 subscales: 1) general mood, 2) breathing problems, 3) hand behavior, 4) face movements, 5) body rocking/expressionless face, 6) night-time behaviors, 7) fear/anxiety, and 8) walking/standing. The total score ranging from 0 to 90 will be calculated as the sum of the scores for all 45 items. Score for item 31 (Uses eye gaze to convey feelings, needs and wishes.) will be reversed (2-observed item score) in the calculation of total score and subscores. Higher total scores indicate greater frequency of symptoms. If there are 9 or less missing item scores, the total score will be calculated by the arithmetic mean of non-missing items multiplied by 45, rounded to the nearest integer. The RSBQ total score will be considered missing if there are missing scores for 10 or more items.

For the calculation of RSBQ subscores, the items under each RSBQ subscore will be summed. If an item is missing it will not be imputed and the subscore will be considered missing.

RSBQ Subscores

- 1) General mood consists of:
 - a. Abrupt changes in mood (Item 14)
 - b. Spells of screaming for no apparent reason during the day (Item 2)
 - c. There are times when she appears miserable for no apparent reason (Item 16)
 - d. Spells of inconsolable crying for no apparent reason during the day (Item 30)
 - e. There are times when she is irritable for no apparent reason (Item 29)
 - f. Screams hysterically for long periods of time and cannot be consoled (Item 22)
 - g. There are certain days/periods where she performs worse than usual (Item 15)
 - h. Vocalises for no apparent reason (Item 36)
- 2) Breathing problems consists of:
 - a. There are times when breath is held (Item 5)
 - b. Swallows air (Item 19)
 - c. Abdomen fills with air and sometimes feels hard (Item 25)
 - d. There are times when breathing is deep and fast (hyperventilation) (Item 1)
 - e. Air or saliva expelled from mouth with force (Item 6)
- 3) Hand behaviors consists of:
 - a. Does not use hands for purposeful grasping (Item 18)
 - b. Restricted repertoire of hand movement (Item 24)

- c. Hand movements uniform and monotonous (Item 20)
- d. The amount of time spent looking at an object is longer than time spent holding or manipulating them (Item 43)
- e. Has difficulty in breaking/stopping hand stereotypies (Item 35)
- f. Has frequent naps during the day (Item 21)

4) Repetitive face movements consists of:

- a. Makes mouth grimaces (Item 28)
- b. Makes repetitive tongue movements (Item 32)
- c. Makes grimacing expressions with face (Item 34)
- d. Makes repetitive movements involving fingers around tongue (Item 4)

5) Body rocking and expressionless face consists of:

- a. Rocks body repeatedly (Item 41)
- b. Expressionless face (Item 12)
- c. Rocks self when hands are prevented from moving (Item 33)
- d. Seems to look through people in to the distance (Item 17)
- e. Uses eye gaze to convey feelings, needs and wishes (reversed) (Item 31)
- f. Tendency to bring hands together in front of chin or chest (Item 40)

6) Night-time behaviours consists of:

- a. Spells of screaming for no apparent reason during the night (Item 13)
- b. Spells of inconsolable crying for no apparent reason during the night (Item 42)
- c. Spells of laughter for no apparent reason during the night (Item 37)

7) Fear/Anxiety consists of:

- a. Spells of apparent panic (Item 38)
- b. Spells of apparent anxiety/fear in unfamiliar situations (Item 7)
- c. Seems frightened when sudden changes in own body position (Item 9)
- d. There are times when parts of the body are held rigid (Item 10)

8) Walking/standing consists of:

- a. Walks with stiff legs (Item 39)
- b. Although can stand independently tends to lean on objects or people (Item 23)

Items not included in Subscores

- a. Makes repetitive hand movements with hands apart (Item 3)
- b. Grinds teeth (Item 8)
- c. Shifts gaze with a slow horizontal turn of head (Item 11)
- d. Spells of laughter for no apparent reason during the day (Item 26)
- e. Has wounds on hands as a result of repetitive hand movements (Item 27)
- f. Appears isolated (Item 44)
- g. Vacant ‘staring’ spells (Item 45)

